5.6.3.4. Procedures for Immune-Mediated Dermatitis

Monitor subjects for signs and symptoms of dermatitis such as rash and pruritus. Unless an alternate etiology has been identified, signs or symptoms of dermatitis should be considered immune-mediated. Recommendations for management of immune-mediated dermatitis are shown in [Table 13](#). If there is any bullous formation, the medical monitor should be contacted and the study drug should be discontinued.

Table 13: Recommended Approach for Handling Dermatitis

Toxicity Grade	Withhold/Discontinue Epacadostat and Durvalumab	Guidance for Restarting Study Treatment	Supportive Care
Grade 1	No action.	Not applicable.	
 For mild to moderate dermatitis, such as localized rash and pruritus, treat symptomatically, including oral antipruritics (eg, diphenhydramine or hydroxyzine) and topical therapy (eg, urea cream). Administer topical or systemic corticosteroids if there is no improvement of symptoms within 1 week.
Grade 2	May withhold epacadostat and durvalumab per investigator discretion.	
If persistent (> 1-2 weeks), hold treatment until resolution to ≤ Grade 1 or baseline.
 
 If toxicity worsens, then treat as Grade 3. If toxicity improves to ≤ Grade 1 or baseline, then resume drug/study regimen after completion of steroid taper. 	
 Obtain dermatology consult. Consider symptomatic treatment including oral antipruritics (eg, diphenhydramine or hydroxyzine) and topical therapy (eg, urea cream). Consider moderate-strength topical steroid. If no improvement of rash/skin lesions occurs within 3-5 days or worsens despite symptomatic treatment and/or use of moderate-strength topical steroid, discuss with medical monitor and promptly start systemic steroids, such as prednisone 1-2 mg/kg per day PO or IV equivalent. Consider skin biopsy if persistent for > 1-2 weeks or recurs.
Grade 3	
Withhold epacadostat and durvalumab.
 
Note: Permanently discontinue epacadostat and durvalumab in subjects with Stevens-Johnson syndrome, toxic epidermal necrolysis, or rash complicated by full thickness dermal ulceration or necrotic, bullous, or hemorrhagic manifestations.
	
Hold treatment until resolution to ≤ Grade 1 or baseline.
 
 If AE resolves within 4 weeks: Restart study treatment at same dose/schedule. If AE does not resolve within 4 weeks: Approval to restart study treatment by medical monitor required; epacadostat will be reduced by 1 dose level, and durvalumab will resume at the same dose/schedule. 	
For Grade 3 or 4:
 
 Consult dermatology. Promptly initiate empiric IV methylprednisolone 1-4 mg/kg per day or equivalent. Consider hospitalization. Monitor extent of rash. Consider skin biopsy (preferably > 1) as clinically feasible. Once improving, gradually taper steroids over ≥ 28 days and consider prophylactic antibiotics, antifungals, and anti-PCP treatment (refer to current NCCN Guidelines for treatment of cancer-related infections [Category 2B recommendation]).
Grade 4	Discontinue epacadostat and durvalumab.	Not applicable.	
 Discuss with medical monitor.

5.6.3.5. Procedures for Immune-Mediated Neuropathies

Subjects should be evaluated to rule out any alternative etiology (eg, disease progression, infections, metabolic syndromes, or medications). Monitor subjects for symptoms of motor or sensory neuropathy such as unilateral or bilateral weakness, sensory alterations, behavior changes, headache, nausea, vertigo, or paresthesia. Consider appropriate diagnostic testing (eg, electromyogram and nerve conduction investigations). Perform symptomatic treatment with neurological consult as appropriate. Recommendations for the management of immune-mediated neuropathies are shown in [Table 14](#).

For any grade immune-mediated peripheral neuromotor syndromes, such as Guillain-Barré syndrome and myasthenia gravis, the following precautions should be followed:

- The prompt diagnosis of immune-mediated peripheral neuromotor syndromes is important, since certain subjects may unpredictably experience acute decompensations that can result in substantial morbidity or, in the worst case, death. Special care should be taken for certain sentinel symptoms that may predict a more severe outcome, such as prominent dysphagia, rapidly progressive weakness, and signs of respiratory insufficiency or autonomic instability.
- Subjects should be evaluated to rule out any alternative etiology (eg, disease progression, infections, metabolic syndromes, and medications). It should be noted that the diagnosis of immune-mediated peripheral neuromotor syndromes can be particularly challenging in patients with underlying cancer, due to the multiple potential confounding effects of cancer (and its treatments) throughout the neuraxis. Given the importance of prompt and accurate diagnosis, it is essential to have a low threshold to obtain a neurological consult.
- Neurophysiologic diagnostic testing (eg, electromyogram, nerve conduction investigations, and "repetitive stimulation," if myasthenia is suspected) is routinely indicated upon suspicion of such conditions and may be best facilitated by means of a neurology consultation.
- It is important to consider that the use of steroids as the primary treatment of Guillain-Barré syndrome is not typically considered effective. Subjects requiring treatment should be started with IVIG, followed by plasmapheresis if not responsive to IVIG.

Table 14: Recommended Approach for Handling Neuropathies

Toxicity Grade	Withhold/Discontinue Epacadostat and Durvalumab	Guidance for Restarting Study Treatment	Supportive Care
Immune-mediated neurotoxicity (to include but not limited to limbic encephalitis, autonomic neuropathy, excluding myasthenia gravis and Guillain-Barré syndrome)			
Grade 1	No action.	Not applicable.	Provide symptomatic treatment.
Grade 2	May withhold epacadostat and durvalumab per investigator discretion.	
 • For acute motor neuropathies or neurotoxicity, hold study treatment until resolution to \leq Grade 1. • For sensory neuropathy/neuropathic pain, consider holding study treatment until resolution to \leq Grade 1. 
 – If toxicity worsens, then treat as Grade 3 or Grade 4. – Study treatment can be resumed once event improves to \leq Grade 1 or baseline and after completion of steroid taper. Epacadostat will be reduced by 1 dose level, and durvalumab will resume at the same dose/schedule. 	
 • Consider systemic corticosteroids in addition to appropriate symptomatic treatment. • If no improvement within 3-5 days despite prednisone 1-2 mg/kg per day PO or IV equivalent, consider additional work-up and promptly treat with additional immunosuppressive therapy (eg, IVIG).
Grade 3 and Grade 4	Discontinue epacadostat and durvalumab.	Not applicable.	
 • Discuss with medical monitor and consider hospitalization. • Obtain neurology consult. • Consider prompt initiation of systemic corticosteroids (IV administration should be strongly considered) at a dose of 1-2 mg/kg per day prednisone or equivalent. • Institute medical intervention as appropriate for management of severe neuropathy. • If no improvement within 3-5 days despite IV corticosteroids, consider additional work-up and promptly treat with additional immunosuppressants (eg, IVIG). • Once stable, gradually taper steroids over \geq 28 days.
Immune-mediated peripheral neuromotor syndromes (eg, Guillain-Barré syndrome and myasthenia gravis)			
Grade 1	No action.	
 • Not applicable. 	
 • Provide symptomatic treatment. • Discuss with the study physician. • Care should be taken to monitor subjects for sentinel symptoms of a potential decompensation as described above. • Obtain a neurology consult, unless the symptoms are very minor and stable.

Table 14: Recommended Approach for Handling Neuropathies (Continued)

Toxicity Grade	Withhold/Discontinue Epacadostat and Durvalumab	Guidance for Restarting Study Treatment	Supportive Care
Grade 2	Withhold epacadostat and durvalumab.	
 • Hold study treatment until resolution to \leq Grade 1. • Permanently discontinue study treatment if it does not resolve to \leq Grade 1 within 30 days or if there are signs of respiratory insufficiency or autonomic instability. 	
 • Discuss with the study physician. • Care should be taken to monitor subjects for sentinel symptoms of a potential decompensation as described below. • Obtain a neurology consult. • Sensory neuropathy/neuropathic pain may be managed by appropriate medications (eg, gabapentin, duloxetine). 
Myasthenia Gravis:
 
 • Steroids may be successfully used to treat myasthenia gravis. Important to consider that steroid therapy (especially with high doses) may result in transient worsening of myasthenia and should typically be administered in a monitored setting under supervision of a consulting neurologist. • Subjects unable to tolerate steroids may be candidates for treatment with plasmapheresis or IVIG. Such decisions are best made in consultation with a neurologist, taking into account the unique needs of each subject. • If myasthenia gravis–like neurotoxicity is present, consider starting acetylcholine esterase inhibitor therapy in addition to steroids. Such therapy, if successful, can also serve to reinforce the diagnosis. 
Guillain-Barré Syndrome:
 
 • Important to consider that the use of steroids as the primary treatment is not typically considered effective. Subjects requiring treatment should be started with IVIG, followed by plasmapheresis if not responsive to IVIG.

Table 14: Recommended Approach for Handling Neuropathies (Continued)

Toxicity Grade	Withhold/Discontinue Epacadostat and Durvalumab	Guidance for Restarting Study Treatment	Supportive Care
Grade 3 or Grade 4	Withhold epacadostat and durvalumab (Grade 3). Discontinue epacadostat and durvalumab (Grade 4).	
 • Hold study treatment until resolution to \leq Grade 1. • Permanently discontinue study treatment if Grade 3 irAE does not resolve to \leq Grade 1 within 30 days or if there are signs of respiratory insufficiency or autonomic instability. 	
 • For severe or life-threatening (Grade 3 or 4) events: 
 • Discuss with study physician. • Recommend hospitalization. • Monitor symptoms and obtain neurological consult. Myasthenia Gravis: 
 • Steroids may be successfully used. They should typically be administered in a monitored setting under supervision of a consulting neurologist. • Subjects unable to tolerate steroids may be candidates for treatment with plasmapheresis or IVIG. • If myasthenia gravis–like neurotoxicity is present, consider starting acetylcholine esterase inhibitor therapy in addition to steroids. Such therapy, if successful, can also serve to reinforce the diagnosis. • Guillain-Barré Syndrome: 
 • Important to consider that the use of steroids as the primary treatment is not typically considered effective. Subjects requiring treatment should be started with IVIG, followed by plasmapheresis if not responsive to IVIG.

IVIG = intravenous immunoglobulin.

5.6.3.6. Procedures for Immune-Mediated Endocrinopathies

Subjects should be monitored for clinical signs and symptoms of hypophysitis, adrenal insufficiency (including adrenal crisis), and hyper- or hypothyroidism. Subjects may present with fatigue, headache, mental status changes, abdominal pain, unusual bowel habits, and hypotension, or nonspecific symptoms that may resemble other causes such as brain metastasis or underlying disease. Unless an alternate etiology has been identified, signs or symptoms of endocrinopathies should be considered immune-mediated. Consult an endocrinologist.

Monitor subjects' thyroid function tests and other relevant clinical chemistries at the start of treatment, every 6 cycles, and as clinically indicated based on symptoms. In a limited number of subjects, hypophysitis was diagnosed by imaging studies through enlargement of the pituitary gland. If a subject experiences an AE that is thought to be possibly of an autoimmune nature (eg, thyroiditis, pancreatitis, hypophysitis, diabetes insipidus), the investigator should send a blood sample for appropriate autoimmune antibody testing.

Treatment may be withheld for \geq Grade 2 events and treatment may be restarted after the initiation of appropriate hormone-replacement therapy. Recommendations are shown in [Table 15](#).

Table 15: Recommended Approach for Handling Endocrinopathies

Toxicity Grade	Withhold/Discontinue Epacadostat and Durvalumab	Guidance for Restarting Study Treatment	Supportive Care
Grade 1	No action.	Not applicable.	
 • Provide symptomatic treatment. • Monitor patient with appropriate endocrine function tests. • If TSH $< 0.5 \times$ LLN, or TSH $> 2 \times$ ULN or consistently out of range in 2 subsequent measurements, include FT4 at subsequent cycles as clinically indicated and consider endocrinology consult (includes those with asymptomatic TSH elevation). • For suspected hypophysitis/hypopituitarism, consider consultation of an endocrinologist to guide assessment of early-morning ACTH, cortisol, TSH and free T4; also consider gonadotropins, sex hormones, and prolactin levels, as well as cosyntropin stimulation test (though it may not be useful in diagnosing early secondary adrenal insufficiency).

Table 15: Recommended Approach for Handling Endocrinopathies (Continued)

Toxicity Grade	Withhold/Discontinue Epacadostat and Durvalumab	Guidance for Restarting Study Treatment	Supportive Care
Grade 2	For endocrinopathy other than hypothyroidism, withhold epacadostat and durvalumab.	
If study treatment is held, resume study treatment at same dose/schedule until subject is clinically stable.
 
 • If toxicity worsens, then treat as Grade 3 or Grade 4. • Study treatment can be resumed once the event stabilizes and after completion of steroid taper. • Subjects with endocrinopathies who may require prolonged or continued steroid replacement can be re-treated with study treatment on the following conditions: 1) the event stabilizes and is controlled, 2) the subject is clinically stable as per investigator or treating physician's clinical judgement, and 3) doses of prednisone are at ≤ 10 mg/day or equivalent. 	
 • Consult endocrinologist to guide evaluation of endocrine function, and as indicated by suspected endocrinopathy and as clinically indicated, consider pituitary scan. • Isolated hypothyroidism may be treated with replacement therapy without treatment interruption and without corticosteroids. • Isolated Type 1 DM may be treated with appropriate diabetic therapy, without study drug interruption, and without corticosteroids. • For subjects with abnormal endocrine work-up, except for those with isolated hypothyroidism, consider short-term, high-dose corticosteroids (eg, methylprednisolone 1-2 mg/kg per day or IV equivalent) and initiate appropriate hormone replacement therapy. • Once improving, gradually taper steroids over ≥ 28 days and consider prophylactic antibiotics, antifungals, and anti-PCP treatment (refer to current NCCN Guidelines for treatment of cancer-related infections [Category 2B recommendation]). • For subjects with normal endocrine work-up (labs or MRI), repeat labs/MRI as clinically indicated.

Table 15: Recommended Approach for Handling Endocrinopathies (Continued)

Toxicity Grade	Withhold/Discontinue Epacadostat and Durvalumab	Guidance for Restarting Study Treatment	Supportive Care
Grade 3 and Grade 4	For endocrinopathy other than hypothyroidism, withhold epacadostat and durvalumab until endocrinopathy symptom(s) are controlled.	
 Study treatment can be resumed once event stabilizes and after completion of steroid taper. 	
 Consult endocrinologist to guide evaluation of endocrine function, and as indicated by suspected endocrinopathy and as clinically indicated, consider pituitary scan. Discuss with medical monitor. Isolated hypothyroidism may be treated with replacement therapy without treatment interruption and without corticosteroids. Isolated Type 1 DM may be treated with appropriate diabetic therapy, without study drug interruption, and without corticosteroids. For all patients with abnormal endocrine work-up, except those with isolated hypothyroidism or Type 1 DM, and as guided by an endocrinologist, promptly initiate empiric IV methylprednisolone 1-2 mg/kg per day or equivalent. For adrenal crisis, severe dehydration, hypotension, or shock: immediately initiate intravenous corticosteroids with mineralocorticoid activity. Once improving, gradually taper immunosuppressive steroids over ≥ 28 days and consider prophylactic antibiotics, antifungals, and anti-PCP treatment (refer to current NCCN Guidelines for treatment of cancer-related infections [Category 2B recommendation])

FT4 = free thyroxine; LLN = lower limit of normal; MRI = magnetic resonance imaging; TSH = thyroid-stimulating hormone.

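### Table 15, Grade 2 row: one word reverses the order of hold and restart, and the steroid bullet omits the Type 1 DM exception given at Grade 3/4

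*Protocol*

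**What the plan says.** Table 15 in Protocol Section 5.6.3.6 has a withhold column, a restart column and a supportive-care column for each toxicity grade.

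**Grade 2, restart column.** The cell opens by saying that, if treatment was held, sites should "resume study treatment at same dose/schedule until subject is clinically stable". A bullet lower in the cell says "Study treatment can be resumed once the event stabilizes and after completion of steroid taper". A further bullet covers subjects who need prolonged or continued steroid replacement. They may be re-treated if the event is stable and controlled, the subject is clinically stable, and "doses of prednisone are at ≤ 10 mg/day or equivalent".

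**Grade 2, supportive-care column.** One bullet reads "Isolated Type 1 DM may be treated with appropriate diabetic therapy, without study drug interruption, and without corticosteroids". The next reads "For subjects with abnormal endocrine work-up, except for those with isolated hypothyroidism, consider short-term, high-dose corticosteroids". The one after that begins "Once improving, gradually taper steroids over" and sets a minimum of 28 days.

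**Grade 3 and Grade 4.** The Type 1 DM bullet is repeated. The steroid bullet then directs prompt intravenous methylprednisolone, and its scope is "For all patients with abnormal endocrine work-up, except those with isolated hypothyroidism or Type 1 DM". The restart cell says "Study treatment can be resumed once event stabilizes and after completion of steroid taper".

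**The concern.** This is not background text. A site opens the table when a subject has an event, to decide whether to dose and whether to give steroids.

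The first sentence in the Grade 2 restart cell gives the wrong order. It has treatment restarting before stability, with stability as the point at which dosing would end.

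The Grade 2 steroid bullet also leaves isolated Type 1 DM inside a prompt to consider high-dose corticosteroids, immediately after a bullet saying the condition may be managed without them. The more severe grades carry the exception and the milder grade does not. Type 1 DM is not a remote case: Protocol Section 1.3.2.2.1 lists it among the risks of durvalumab monotherapy.

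What is at stake is the safety and consistency of individual management, not the efficacy analysis.

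**Working it through.** The plan gives no figure on this point, so there is nothing to recalculate. The check is to set the instructions side by side.

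**Restart order**

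- Table 15, Grade 2, lead sentence: restart first, with stability as the end of the interval.
- Same cell, later bullet: event stable and taper complete, then restart.
- Same cell, continued-steroid bullet: event controlled, subject stable and prednisone at or below 10 mg/day, then re-treat.
- Table 15, Grade 3/4: hold until symptoms are controlled, then restart after stabilization and taper.
- Section 5.6.3.6, text before the table: restart follows the start of hormone replacement.
- Table 16 (nephritis), Grade 2: an almost identical sentence, but with *when* and control of the event.
- Section 5.6.3.12, general rule for immune-related events: treatment may resume when listed conditions have been met.

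The lead sentence stands alone against the other six. No sensible reading rescues *until*, because a hold imposed for an unstable event cannot be lifted only for as long as the event stays unstable. The Table 16 sentence suggests that *when* or *once* was meant.

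**Corticosteroids for isolated Type 1 DM**

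- Grade 2, Type 1 DM bullet: may be treated without them.
- Grade 2, steroid bullet: consider them for any abnormal endocrine work-up; the only exception is isolated hypothyroidism.
- Grade 3/4, Type 1 DM bullet: may be treated without them.
- Grade 3/4, steroid bullet: start them promptly; the exceptions are isolated hypothyroidism and Type 1 DM.

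An isolated Type 1 DM case with an abnormal work-up is therefore inside the Grade 2 steroid bullet and outside the Grade 3/4 one. The Protocol gives no reason for a narrower exception at the lower grade.

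**Related location**

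Table 21, Grade 2, repeats the three endocrinopathy re-treatment conditions of Table 15 but prints the prednisone condition as ≥ 10 mg/day. Table 15 prints ≤ 10 mg/day, and the Section 5.6.3.12 text that introduces Table 21 also uses ≤ 10 mg/day. As printed, Table 21 would make a higher steroid dose a requirement for restarting.

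**The case against.** The best reply is that the table corrects itself. The right restart order stands two bullets below the slip, and the literal reading makes no sense beside the withhold cell in the same row. Section 5.6.3 requires events of Grade 2 or higher to be discussed immediately with the medical monitor, and the Grade 2 row calls for an endocrinology consult. This stands, and it is why the point is minor. It lowers the chance that a site acts on the wrong sentence; it does not make the sentence right.

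On steroids, the Grade 2 bullet says only to consider them, whereas the Grade 3/4 bullet directs prompt treatment, so an explicit exception matters more at the higher grades. The Type 1 DM bullet can also be read as a specific carve-out. That too has force: the two Grade 2 bullets are permissive and do not flatly contradict each other. But the exception is spelled out in one row and left to inference in the other, with no stated reason.

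Table 21 covers events not described in earlier sections, so Table 15 governs endocrinopathies whatever Table 21 prints. That is correct, and the Table 21 sign is treated here only as a conforming edit.

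A reader might go further and infer that the Grade 2 steroid bullet costs subjects with Type 1 DM a hold of at least 28 days and several missed doses. The documents do not support that. It would need steroids to be chosen despite the Type 1 DM bullet, a time to improvement that is nowhere given, and a completed taper before restart. The continued-steroid bullet shows that a completed taper is not always required. Nor does Section 5.6.2 set a 4-week cap on interruptions: its sentence on longer interruptions requires a discussion with the medical monitor before resuming.

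A reader might also call the Grade 2 withhold cell wrong because it excepts only hypothyroidism. The Type 1 DM bullet can be read as a specific exception to that cell, so no error is claimed there.

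**Conclusion.** Wrong as written, minor severity. The Grade 2 row of Table 15 has two wording errors in operative guidance: a reversed restart order in the lead sentence, and a missing Type 1 DM exception in the steroid bullet. Both follow from direct comparison of the text and rest on no numerical assumption. The intended order is plain from the surrounding instructions. That the missing exception was unintended is an inference from the Grade 3/4 wording and the adjacent Type 1 DM bullet.

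The size cannot be put in doses or subjects: the documents give neither the number of Grade 2 endocrinopathies expected nor the length of a hold. It would also go too far to infer that the Protocol lacks safeguards or that subjects will be dosed while unstable, given the limits described above. Objective response rate, sample size and error rates are unaffected.

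**What to change.** Make two edits in the Grade 2 row of Table 15:

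1. In the lead sentence of the restart cell, replace *until* with *once*. Leave the bullets below as they are. A completed taper and continued prednisone at ≤ 10 mg/day are alternative routes to restarting, and wording that requires all the listed conditions together would bar subjects on continuing steroid replacement whom the cell expressly allows.
2. In the steroid bullet, add *or Type 1 DM* after isolated hypothyroidism, matching the Grade 3/4 row.

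Conforming edit: in Table 21, Grade 2, change the endocrinopathy prednisone condition from ≥ 10 to ≤ 10 mg/day, after confirming the sign against the source file.

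The cost is a few words and one symbol, which can go into the next amendment or a clarification to sites. No visit, data collection or analysis changes.
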